The primary endpoint of this study will be the rate of adherence compared between the two groups. Secondary endpoints include rates of COPD related hospitalization or death, activity levels as measured by the average number of steps per day, and the CRQ scales of dyspnea, fatigue, emotional function, physical, mastery, and the total score. Differences between groups will be compared with Fisher’s exact tests for proportions and ttests for continuous endpoints. These analyses will be supplemented with logistic regression models and linear models to compare groups after adjusting for confounding factors.

One hundred and forty-four patients will be entered on this study (72 per arm). After adjusting for multiple comparisons, this sample size will provide at least 80% power to detect a difference in the rates of adherence of 26% in the control group to 50% in the intervention group. This sample size will also provide at least 80% power for detecting a 50% reduction in hospitalization/death rates (from 50% in the control group at 6

months to 25% in the intervention group at 6 months), a difference of 1000 steps at 3 months (assuming a standard deviation [SD] of 2,000 steps), and a 0.5 difference in CRQ summary scores at 3 months (assuming an SD of 1.0). The sample size will be increased to 150 (75 per arm) to account for a 5% drop out rate.

Outcomes for the Phase 2 Randomized study

Aim 3a: Adherence will be our primary outcome

Overview: The reported adherence for PR after a hospitalization is 4% and in the best case scenario (free PR and free transportation like in the UK) is 10%. From our preliminary data, now in press (Respiratory Care), we found an adherence of >80% to the proposed system in outpatients with COPD. We hypothesize the adherence to a complete home-based PR program by post-hospitalized patients will be around 50%, and the adherence to the conventional hospital-based PR program to be 25% (due to our strong efforts to encourage people attend) will consider a complete PR when 75% of the expected PR visits are completed. We will compute the degree of completion of conventional PR from our electronic health record (EHR). The home-based PR compliance will be assessed by the entries of the PR coach in REDCap.

Aim 3b: CRQ Physical and Emotional Summary scores post PR

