Assessment of Bias: Potential bias due to loss to follow-up will be assessed using a time to event analysis for the association of patient characteristics with time to dropout; results will be reported and used to evaluate the robustness of the study findings. We will also conduct sensitivity analyses in which missing data for dropouts are imputed under plausible missing-not-at-random assumptions.

Missing data: A common affliction with randomized clinical trial field experiments is noncompliance with both treatment and missing study participation data. To estimate the overall treatment effect for the entire sample, an "intention to treat" analysis will be conducted, using our above likelihood-based analysis method for repeated measures, including data on all subjects who were randomized to the study group. This allows us to use all available data, rather than delete participants with missing values from the analysis of treatment effects.³⁴

Aim 4: Cost-Effectiveness Analysis

This aims to estimate the value of implementing Home PR compared to subjects referred to conventional PR. The CEA, will estimate the ratio of the average change of cost per patient divided by the average change in QALYs per patient for health coaching compared to delivering standard care. QALYs will be based on the EQ-5D-3L³⁵ using a preference-based value set derived from a sample of the US population. QALYs will be calculated by multiplying the utilities by a number of time participants spent in a particular health state. Transitions between health states will be linearly interpolated. The perspective for the CEA is that of the healthcare provider.

For both arms, all resource utilization at the health centers for the one-year period following index hospitalization discharge will be collected. Estimated costs will be standardized using a bottom-up approach. Professional services defined by Current Procedure Terminology code will be valued using national reimbursement amounts from the Medicare fee schedules. Billed charges for hospital services will be valued using department specific cost-to-charge ratios based on the hospital's annual Medicare cost report. All costs will be inflated to a common year using the Gross Domestic Product implicit price deflators.

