Multivariate regression models will be employed to control for differences between study groups. Due to the highly skewed nature of healthcare costs, a generalized linear model incorporating a gamma distribution and log-link function will be used. The cost-effectiveness of the home PR intervention will be determined using the threshold of \$50,000/QALY. The 95% CI of the cost-effectiveness ratio will be calculated using nonparametric bootstrapping.

Healthcare utilization occurring at facilities outside of our network will not be captured. Sensitivity analysis of the cost-effectiveness will be performed based on residency status (local, regional, and distant).

Limitations: We acknowledge that comparing to completed regular PR would be ideal, however, given that the completion rate post-hospitalization is so low, accruing for such a study would be unrealistic. We strongly believe that the proposed design truly represents “a real world” study and the result from it would be applicable to the practicing clinicians and regulatory agencies and payers to further support alternative ways of PR (if our hypothesis is confirmed: increased adherence, decreased readmission and patients’ critical outcomes like daily physical activity and quality of living). We will put a dedicated effort to motivate individual to attend conventional PR if they are randomized to arm.

We will not know if the improvement in adherence is because of the home-based PR or health coaching. However, given that, only 4% complete conventional PR after a hospitalization, a meaningful improvement in adherence would not require much effort from the patients the home-based PR program.

R61 milestones (two years)

Year 1

1. Finalization of the protocol and the informed consent document
2. Development of the manual of operations and case report forms
3. Establishment of a Data and Safety Monitoring Board
4. Institutional Review Board approval of the trial
5. Pilot cohort of 10-15 patients to refine the intervention already developed for outpatients
6. Qualitative study and application of the necessary changes to the proposed Home PR

Year 2

Begin enrollment into the clinical trial to allow for an evaluation by the end of the R61 phase of early enrollment and the probability of completing the trial on time and budget. Target for year two will be to recruit 30 of 150 subjects planned for the whole study.

R33 milestones

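### The planned bootstrap interval for the cost-effectiveness ratio has no rule for replicates with a zero or negative QALY difference; adding net monetary benefit at the plan's own threshold would fill the gap

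*Combined protocol and SAP*

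**What the plan says.** Under Aim 4: Cost-Effectiveness Analysis, the result is defined as a ratio: "The CEA, will estimate the ratio of the average change of cost per patient divided by the average change in QALYs per patient", for the intervention against standard care. The horizon is one year: "all resource utilization at the health centers for the one-year period following index hospitalization discharge will be collected". Costs are described as highly skewed, and "a generalized linear model incorporating a gamma distribution and log-link function will be used".

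Two consecutive sentences then give the decision threshold and the interval. The first reads "The cost-effectiveness of the home PR intervention will be determined using the threshold of" $50,000/QALY. The second reads "The 95% CI of the cost-effectiveness ratio will be calculated using nonparametric bootstrapping".

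The section does not name the type of bootstrap interval (percentile or other). It has no rule for replicates in which the QALY difference is zero, near zero or negative. It does not mention net monetary benefit, a cost-effectiveness plane, an acceptability curve or Fieller limits.

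The sample size comes from Statistical Analysis and Power: "One hundred and forty-four patients will be entered on this study (72 per arm"), raised to 75 per arm for dropout. It is justified on adherence, hospitalization or death, steps and CRQ. No SD, expected difference or power is given for QALYs or costs.

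**The concern.** A ratio of two differences can be read on one scale only while its denominator keeps one sign. If bootstrap replicates fall on both sides of zero QALY difference, two things go wrong. A negative ratio can mean that home PR is cheaper and better, or dearer and worse. A positive ratio below $50,000 can mean a worthwhile gain at modest cost, or a health loss that saves too little. The ratio also jumps between plus and minus infinity as the denominator passes through zero. Sorting such values and taking limits does not give a range that runs from favourable to unfavourable.

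At stake is how the uncertainty around the Aim 4 threshold conclusion is described. The plan addresses its results to payers among others, and a reader would naturally set the printed interval against $50,000.

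**Working it through.** **1. Inputs.** From the documents: 72 per arm, $50,000/QALY, one-year horizon, skewed costs. There is no planned QALY precision to reproduce, so only the sample size can be checked. For 26% against 50%, two-sided 5% and 80% power, the continuity-corrected formula gives 72 per arm, as stated, and Fisher's exact power at 72 is 80.7%. The dropout step gives 144/0.95 = 151.6, so 152 against the stated 150. The Data Analysis Plan paragraph gives a different control rate (6%) but the same 72 per arm, which is all that is used below.

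**2. The reversal, which needs no assumed SD.** Write dC and dQ for the cost and QALY differences, and NMB = 50,000 × dQ − dC.

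- If dQ > 0: dC/dQ < 50,000 is equivalent to NMB > 0.
- If dQ < 0: multiplying by a negative number flips the inequality, so dC/dQ < 50,000 is equivalent to NMB < 0.

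Example: (+$500, +0.02 QALY) gives 500/0.02 = $25,000/QALY and NMB = 1,000 − 500 = +$500. (−$500, −0.02 QALY) also gives $25,000/QALY, but NMB = −1,000 + 500 = −$500. The ratio is the same and the conclusions are opposite.

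**3. How often this would occur.** The standard error (SE) of dQ is SD × √(2/72) = SD/6. The share of replicates with dQ below zero is about Φ(−gain/SE), with replicates centred on the estimated gain. The SDs and gains are assumptions.

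| Estimated gain (QALY) | SD 0.10 (SE 0.0167) | SD 0.20 (SE 0.0333) | SD 0.25 (SE 0.0417) |
|---|---|---|---|
| 0 | 50% | 50% | 50% |
| 0.01 | 27% | 38% | 41% |
| 0.03 | 4% | 18% | 24% |
| 0.05 | 0.1% | 7% | 12% |
| 0.10 | about 0 | 0.1% | 0.8% |
| 0.15 | about 0 | about 0 | about 0 |

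For example, at gain 0.03 and SD 0.20: 0.03/0.0333 = 0.9 and Φ(−0.9) = 18%.

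**4. Simulation.** There were 1,500 trials of 72 per arm with 1,000 nonparametric bootstrap replicates each, using percentile limits and unadjusted means. Assumed: gamma costs with control mean $20,000 and coefficient of variation (CV) 1.0, cost difference +$2,000, QALY SD 0.20, cost–QALY correlation −0.3. A trial counts as straddling zero if between 2.5% and 97.5% of its replicates have dQ at or below zero.

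| True gain | Trials straddling zero | Median ratio interval width ($/QALY) | Ratio coverage | NMB coverage |
|---|---|---|---|---|
| 0 | 95% | 2.49 million | ratio undefined | 94.3% |
| 0.01 | 93% | 2.45 million | 94.6% | 94.5% |
| 0.03 | 86% | 2.19 million | 98.3% | 95.1% |
| 0.05 | 67% | 1.23 million | 98.0% | 95.3% |
| 0.10 | 13% | 208,000 | 96.2% | 95.0% |
| 0.15 | 0.6% | 107,000 | 95.0% | 94.8% |

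The median NMB interval width was about $16,300 to $16,400 in all six rows. Three variants at a true gain of 0.03 (cost difference −$4,000; cost CV 1.5; QALY SD 0.10) gave straddling in 84%, 86% and 56% of trials. Their median ratio widths were $1.92, $3.05 and $1.53 million. Ratio coverage was 96.7%, 98.8% and 97.0%, and NMB coverage 92.4%, 94.4% and 94.3%.

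**The case against.** Four objections have force.

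**The conclusion need not rest on the interval.** A reader might infer that Aim 4 is decided by comparing the interval, or each replicate, with $50,000. The plan does not say so. The threshold and the interval are in separate sentences, and the natural reading is that the point estimate is set against the threshold. This stands: the defect lies in how uncertainty is reported, not in a stated decision rule.

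**The interval type is not stated.** The simulation uses percentile limits, a plausible default, but bootstrap limits can also be set with replicates ordered by quadrant. This stands too. It does not remove the gap, because the plan gives no ordering rule.

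**The interval is not shown to be invalid.** A reader might take its width and mixed quadrants to mean that it misses the true ratio too often. It does not: where the true ratio exists, coverage was 94.6% to 98.8%, against 92.4% to 95.3% for net benefit. With skewed costs, net benefit can fall slightly short of nominal coverage.

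**The condition may not arise.** The documents give no figure that settles the size of the QALY gain, and the plan's own planning effect is large (hospitalization or death from 50% to 25% at 6 months). At gains of 0.10 to 0.15 the problem largely fades. This stands as a limit on the point. Against it, the trial is not sized for QALYs, and some passages suggest that controls later receive the intervention (a wait-arm label, and a planned description of the home intervention's effect on controls) while others describe referral only. A crossover would pull the one-year difference towards zero. Those passages should be reconciled.

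**Conclusion.** The point holds in a conditional form. The plan sets a bootstrap interval on the ratio and gives no handling for replicates with a zero or negative QALY difference, where the ratio is undefined or its comparison with $50,000 is reversed. With 72 per arm and an assumed SD of 0.20, the interval is likely to be uninterpretable for gains up to about 0.05 QALY, with median simulated widths of about $1.2 to $2.5 million per QALY. It is usually usable at 0.10 to 0.15 or more. A smaller SD shrinks the problem: at a gain of 0.03, 4% of replicates are negative with SD 0.10, against 24% with SD 0.25.

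The algebra in step 2 rests on no assumption. The frequencies and widths rest on assumed SDs, gains, costs and correlation, and the simulation did not include the plan's covariate-adjusted models. The documents do not support the further step of dropping the ratio as the Aim 4 result, since it is the plan's stated estimand and remains a proper point estimate. Aim 4 is neither the primary endpoint nor a powered one. This is an inexpensive improvement that should be made before analysis, and it does not threaten the trial's main conclusion.

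**What to change.** In the Aim 4 section:

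- Keep the ratio of mean cost difference to mean QALY difference as the point estimate.
- From the same bootstrap replicates, also compute incremental net monetary benefit (50,000 × QALY difference − cost difference). Report it with its bootstrap 95% interval as the measure of uncertainty for the threshold conclusion. Name the interval type, and refit the adjusted cost and QALY models in each replicate.
- Give no percentile interval for the ratio when replicates cross zero QALY difference, and define crossing in advance. The 2.5% to 97.5% criterion in the simulation is one option. Crossing zero cost difference alone does not reverse the threshold comparison and need not trigger the rule.
- A cost-effectiveness plane or acceptability curve is optional.

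The cost is a few sentences in the SAP and a little extra analysis and reporting, with no new data. Net benefit depends on the chosen threshold, and its interval covers sampling error only. It does not repair the out-of-network utilization that the plan says will not be captured, or missing EQ-5D data.

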During the consent process, the patient will have the opportunity to try the proposed home-based PR system in the hospital room, aiding in their confidence in their ability to use the system and the ease of the exercises. The study team will provide a step by step demonstration of the exercises (following the exercises on the computer tablet). The participant will be asked to rate their confidence to use the technology presented and their confidence (self-efficacy) to perform the home rehabilitation routine on a scale from 0 (no confidence) to 10

(great confidence). A rating of five or greater will be deemed an acceptable confidence level to participate in the study.

Each participant will be asked to define a particular place and time they can perform the home-based PR. The physical and mental environment is critical for the successful adoption of new behavior (PR). Participants will learn about the weekly calls with the coach to discuss their rehabilitation and monitored measures (steps, level of shortness of breath, well-being, and fatigue). They will then go over the daily answers to well-being questions (mood, breathlessness, and energy, as tested in the pilot study and shown in Fig.2; see participant software application section below). After performing the PR routine (to ensure safety and understanding) and reviewing the use of the monitors, a plan for a PR coach call, a week to 10 days after discharge. The participant will use the criterion activity monitor (Actigraph, Fig. 3) that will determine the baseline physical activity during the first week immediately after discharge to define a baseline physical activity. The coordinator will discuss the in-home activities with the participant to identify possible exercise-related fall hazards in the home environment.

[figure not shown]

Figure 2

Figure 3

Figure 4

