feedback plus SM: After the hospital and consenting visit, coaching calls will occur weekly for twelve weeks following this protocol: (1) Listen to the participant’s journey. (2) Provide feedback of the PR process at home based on the feedback from the coach application. Sessions will generate dialogue by listening to “change participant’s comments on anticipated activities. (3) If problems arise, resist the urge to attempt to solve the participant’s problems and barriers. (4) Listen carefully and kindly (ambivalence from the participant in changing their behavior). (5) Discuss how behaviors connect to the participant’s values and strengths. (6) Collaborate in setting goal(s) for the following week. A goal can be anything the patient wants to discuss even beyond PR (like smoking cessation, vaccinations, weight loss, etc.) (7) Discuss the process of action planning: elicit the participant’s preferences. (8) Elicit the participant’s choice; do not assign goals, and use the participant’s language to describe the goal. (9) Assess confidence for goal completion, reaffirm commitment to the action plan, and express optimism. (10) Thank the participant and plan the next call. (11) All calls will be recorded to ensure **fidelity** and **compliance** with the protocol and MI principles (10% of all calls will be reviewed).

Health Coach Software Application: The health coach software application provides three types of reports. The overview report (Fig. 8) allows health coaches to succinctly ascertain the status of their participants and flag anyone who may be experiencing problems. The health coach may select a participant from the overview to display the trend report (Fig. 9). The trend report allows the health coach to review the participant’s progress between weekly health coaching sessions. Finally, the health coach may select a day from the trend report to display a detailed report (figure 10).

Subjects		Alerts	Messages	Display			
Subject ID	Activity Monitor		Exercise and Walking			Check-In Questionnaire	
	Synchronized	Ave Step Count	Performed	Pulse Ox	Ave Duration	Answered	Concerns
pr10001	3 Days Ago	1402	2 Days Ago	●	4.4	2 Days Ago	●
pr10002	4 Days Ago	7900	5 Days Ago	●	8.4	5 Days Ago	
pr10003	Yesterday	10200	7+ Days Ago		0.0	7+ Days Ago	
pr10004	7+ Days Ago	0	7+ Days Ago		0.0	7+ Days Ago	
pr10005	5 Days Ago	0	7+ Days Ago		0.0	7+ Days Ago	
pr10006							
pr10007	Yesterday	9733	Yesterday	●	17.2	Yesterday	

[figure not shown]

Figure 8

Figure 9

Figure 10

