While participant monitoring does not occur in real time, any significant physiologic abnormality measured during rehabilitation and transmitted to the server (O₂ saturation less than 80% or heart rate greater than 140 or less than 40 beats per minute) prompts a message to the coach to call the participant to investigate the event. The PI also is alerted within 24 hours by text message if a physiologic abnormality is measured to ensure the appropriate response. In R44HL114162-03 Home-Based Health Management of COPD Patients, the remote rehabilitation and health coaching system has been pilot tested together and found feasible, actionable, and acceptable. After the pilot is completed, a qualitative study will be done to identify areas of deficits to be changed and then adapted for the second phase of the study, a randomized control trial.

Phase 2 (R61): Mayo Clinic Rochester and Jacksonville Fl will participate in this Phase. Phase 2 will take part in year 2 of the study. After the study has been refined in Phase 1, thirty (30) participants (of the planned 150 subjects) will be recruited and randomized to one of two to the home-based PR or referred to conventional PR (standard of care). After the 30 subjects are enrolled, the study staff will review the feasibility, informing the team about accrual and outcome completion rate (questionnaires and activity monitors). This will allow the study team to forecast a complete and informative study for the R33.

The participants randomized to control/conventional care will be offered mileage reimbursement to and from a pulmonary rehab center. The mileage rate used will be the current IRS standard rate (57.5 cents per mile in 2020). The study will pay mileage up to a total of \$500. Study staff will use MapQuest to determine the miles from participants residence to the rehab center. The participants will be asked to sign an Authorization to Release Protected Health Information-Research in order to obtain Pulmonary Rehabilitation Records. Mileage will be paid monthly when possible, or when in receipt of the medical records confirming attendance.

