The PHQ9 will be reviewed by study staff within 24 hours of receiving the questionnaire in the mail. The study staff will score the PHQ9 and a total score >14 (15 and above) and Item 9 is a zero will prompt a review of medical records for current mental health treatment (in consultation or pharmaceutically) of depression. If the patient is not being treated for mental health issues a licensed health care provider will contact the patient and offer a referral or other treatment suggestions. If anything other than “not at all” on Item 9 “Thoughts that you

would be better off dead or of hurting yourself in some way? The participant will be called by a licensed health care provider.

Health Care Utilization: The Study Coordinator will contact all participants at Months 3,6 and 12 via telephone to determine health care utilization, the participants will be asked how many times they have gone to the doctor/Emergency Room/Hospital for breathing problems. In addition, the participants will be asked if they have taken antibiotics or prednisone for breathing related illnesses since the last time the Study Coordinator called them.

Conventional PR group: Referral to Conventional PR (retention strategies)

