We plan to optimize the possibility of patients referred to conventional PR to attend by generating a dialogue about the importance of PR, facilitating the referral and then follow up with a call. This optimization initiative includes targeting the most prevalent problems that explain the current poor utilization of the traditional hospital-based PR after a hospitalization: (1) lack of a referral or strong recommendation from a physician (we plan to do a dedicated referral to the [patient indicating the nearest PR program and contact information including the proper referral order), and (2) inadequate follow-up or facilitation of enrollment after referral (we will communicate with the individuals two weeks after discharge to encourage PR program adherence). Finally, we acknowledge that many patients/caregivers will clearly express being unable to attend conventional PR and realize then that the control arm receive no active intervention. The latter is a significant problem in behavioral interventions that cannot be blinded. *To palliate that problem* and given that the project targets daily physical activity, we will provide every individual in the conventional PR group a Garmin Vivofit (Fig. 3), an activity monitor that has a large display and is easy to use so that they can monitor steps every day. We have ample experience on the use of this monitor in current pour proposal. This is the same monitor that individuals in the Home PR receive for daily use. The study does not cover standard of care treatment. **Home PR group: Proceedings will be as in the pilot study plus refinement (see R61, Phase 1 and 2).**

Recording of calls and qualitative interviews: All health coaching calls and the qualitative interviews will be recorded. The health coaching calls are recorded and the voice file saved on a secure research drive that only study team has access too. The files are saved under the participants subject number and the week of the call. The calls are randomly selected to be reviewed by the PI [name] and the Fidelity Officer, [name]. Dr.'s [name] and [name] will score the health coach using the MITI worksheet (attached, Appendix 1). The voicefiles will be deleted off of the research drive at the end of the study.

Resources:

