Meeting the projected recruitment for all study participants, including women and minorities (50 subjects per year).

1. Year 3 – 80/151 subjects recruited,
2. Year 4 – 130/151 subject recruited;
3. Year 5 – 151 of 151 subjects recruited, Database lock and analysis, Submission of the primary manuscript(s) to peer-reviewed scientific journal(s) and dissemination of results including the submission of study results to ClinicalTrials.gov within 12 months of the primary completion date.
4. **All years milestones** – Report of monitoring protocol implementation and collection of data related to primary and secondary endpoints and adverse events.

BIBLIOGRAPHY

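### By month 3 the home arm has 13 scheduled study calls and the control arm 2, with no written question to either about falls or other non-respiratory events, so by-arm counts of those not reaching hospital are open to ascertainment bias

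*Combined protocol and SAP*

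**What the plan says.** All references are to the combined protocol and SAP.

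- **Commitment.** R33 milestones, all years: "Report of monitoring protocol implementation and collection of data related to primary and secondary endpoints and adverse events". This is the only mention of adverse events. No definition, question, time window or analysis follows.
- **Home arm.** Coaching PR Calls (weeks 1-12): "After the hospital and consenting visit, coaching calls will occur weekly for twelve weeks following this protocol". The paragraph before Phase 2 (R61) adds that a low saturation or an abnormal heart rate transmitted from a rehabilitation session leads the coach to telephone the patient.
- **Control arm.** Conventional PR group: "we will communicate with the individuals two weeks after discharge to encourage PR program adherence".
- **Both arms.** Health Care Utilization: "The Study Coordinator will contact all participants at Months 3,6 and 12 via telephone to determine health care utilization". The content is that "the participants will be asked how many times they have gone to the doctor/Emergency Room/Hospital for breathing problems", plus a question on antibiotics or prednisone for breathing illness. Aim 3d describes the utilization calls as scripted and made by a blinded coordinator, uses the EHR as well, and states that emergency visits and hospitalizations from any cause are recorded.
- **Falls.** At the consent visit (Study Design and Methods) the coordinator is to "identify possible exercise-related fall hazards in the home environment". No later question about falls appears.

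**The concern.** An event that nobody asks about is recorded only if the patient volunteers it, and patients volunteer more when they are called more. Here one arm is called weekly by a coach who opens by listening to how things have gone, and the other is called once about attending rehabilitation. A fall at home that needs no hospital visit has many chances to reach the study in the first arm and few in the second.

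The Limitations paragraph expects the results to inform clinicians, regulators and payers. If the reported adverse events are tabulated by arm, an excess of falls or minor injuries under home rehabilitation could be an artefact of contact. A low count could equally mean that nobody asked. Neither result would say much about how exercise without on-site supervision is tolerated after discharge.

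**Working it through.** The plan states no contact total and no adverse-event rate, so there is no figure of its own to reproduce.

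**1. Scheduled study calls to month 3**

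- Home: 12 weekly coach calls + 1 month 3 call = 13.
- Control: 1 two-week call + 1 month 3 call = 2.
- Ratio: 13 / 2 = 6.5. Alert-triggered calls in the home arm are extra and not counted.

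**2. Which events depend on those calls**

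| Event | Home arm | Control arm |
|---|---|---|
| Breathing-related visit, antibiotics, prednisone | Common call; EHR for admissions | Same |
| All-cause emergency visit or admission within Mayo | EHR | Same |
| Non-respiratory emergency visit or admission elsewhere | Not in the written questions; may reach the coach | Not in the written questions |
| Fall, injury or other non-respiratory event without a hospital visit | Volunteered over 13 calls | Volunteered over 2 calls |
| Desaturation or abnormal heart rate in a session | Oximeter alert | No equivalent |

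Only the last three rows depend on arm.

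**3. Size under equal true rates (illustration)**

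Assumptions, none of them in the documents: event times are uniform over 91 days; each call after the event brings it to light with probability q, independently; home calls fall on days 7, 14, ..., 84 and 91; control calls fall on days 14 and 91.

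- Home: the 13 seven-day intervals leave 13, 12, ..., 1 calls to come, so detection = 1 - (1/13) × Σ(1-q)^k for k = 1 to 13.
- Control: detection = (14/91) × [1-(1-q)²] + (77/91) × q.

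At q = 0.5:

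- Home = 1 - 0.9999/13 = 0.923.
- Control = 0.1538 × 0.75 + 0.8462 × 0.5 = 0.538.
- Ratio = 0.923 / 0.538 = 1.71.

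The last three columns give the chance of a two-sided 5% Fisher exact result with 75 per arm, by exact binomial enumeration, for true event rates of 10%, 20% and 30%.

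| q | Home | Control | Ratio | 10% | 20% | 30% |
|---|---|---|---|---|---|---|
| 0.10 | 48% | 11% | 4.25 | 7.7% | 33.7% | 58.6% |
| 0.25 | 77% | 28% | 2.78 | 14.5% | 42.1% | 64.4% |
| 0.50 | 92% | 54% | 1.71 | 8.1% | 19.7% | 33.0% |
| 0.75 | 97% | 78% | 1.25 | 3.8% | 6.3% | 9.4% |
| 1.00 | 100% | 100% | 1.00 | 2.7% | 3.1% | 3.3% |

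The Methods allow the first coach call as late as day 10. With calls on days 10, 17, ..., 87 and 91 and q = 0.5, the home miss rate is [10 × 0.5^13 + 7 × (0.5 - 0.5^12) + 4 × 0.5] / 91 = 5.50/91 = 0.060. The ratio is then 0.940 / 0.538, about 1.74, so the result hardly moves.

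**4. With one identical question at the month 3 call only**

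Detection is q in both arms, so the expected ratio under no true difference is q/q = 1.0. Over the same grid the Fisher false-positive rate is at most about 3.3%.

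**The case against.** The strongest reply is that the important harms are already handled evenly. Aim 3d uses the EHR and scripted calls by a blinded coordinator and records all-cause emergency visits and admissions, and COPD-related hospitalization or death is a secondary endpoint in both arms. This stands. A reader might infer that every comparison of harm between arms is biased, or that no common question is asked at all; the documents do not support either. One gap remains: the written call questions cover breathing only, so non-respiratory events treated outside Mayo may be missed.

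Other points on that side:

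- **Unseen material.** Case report forms, a manual of operations and a data and safety monitoring board are separate year 1 milestones, and an adverse-event form may exist. A reader might infer that the board sees nothing comparative, because the review after 30 patients is described as one where "the study staff will review the feasibility, informing the team about accrual and outcome completion rate (questionnaires and activity monitors". That sentence describes a feasibility review and says nothing about what the board receives. A form alone would not equalize contact.
- **Control contact outside the study.** Controls who attend center-based rehabilitation are seen by staff, and the study obtains those records. Aim 3a expects about 25% to complete. This narrows the gap for attenders only.
- **Contacts after month 3.** A reader might extend the count to month 12 as 13 + 2 = 15 against 2 + 2 = 4. That is unsafe. The Questionnaires paragraph times the alliance questionnaire to the end of coaching and gives it at month 6 in a Control/Wait arm, and Analyses refers to the home intervention's effect on the control arm. If controls receive 12 calls after month 3, their total is 4 + 12 = 16.
- **The coach script.** A reader might take the instruction not to solve patients' problems as suppressing reports. It concerns coaching style and does not bar recording an event.
- **Named risks.** Falls are not the only exercise risk foreseen; desaturation and heart-rate limits are named too, with monitoring in the home arm only.
- **No planned test.** The SAP plans no between-arm adverse-event analysis. That is true, but the milestone requires reporting, and a by-arm listing invites the comparison.

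**Conclusion.** The point holds in a limited form. As written, the plan gives arm-dependent capture of falls and other non-respiratory events that lead to no recorded emergency visit or admission. The contact imbalance to month 3, 13 against 2, comes directly from the documents.

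The size of the bias does not. It rests on the assumed per-call detection probability and runs from a ratio of 4.25 at 10%, through about 1.7 at 50%, to 1.0 at complete detection. With no scripted question a low probability is plausible, but that is a judgement.

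COPD-related and all-cause hospitalizations, emergency visits and deaths are not in question, apart from non-respiratory events outside Mayo. Adherence, the primary endpoint, and the sample size are untouched.

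**What to change.** 1. Add the same short scripted items to the month 3, 6 and 12 calls in both arms: any fall, any injury, any other new health problem, and any emergency visit or hospitalization for any reason. Word them so that the answers do not reveal the arm to the blinded coordinator, which rules out asking whether the event happened during exercise.
2. Base between-arm safety comparisons on the month 3 answers, plus deaths and all-cause emergency visits and hospitalizations.
3. Treat months 6 and 12 as descriptive until the Control/Wait wording under Questionnaires and the matching sentence in Analyses are reconciled with the rest of the design.
4. List events learned from coach calls and oximetry alerts separately, labelled as home-arm-only data.

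The cost is about a minute on calls already scheduled, and a shorter list of events that can be compared between arms. If the case report forms already contain such items, it is enough to cite them in the protocol and confirm that both arms are asked at the same calls.
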